4.3. Exploratory Objectives

Table PYAH.4.5. Exploratory Objective of Study J2X-MC-PYAH, Treatment Arms 1-6

The exploratory objective is	
Characterize emergence of viral resistance to LY3819253 and LY3819253 in combination with LY3832479	Comparison from baseline to the last evaluable time point up to Day 29

Table PYAH.4.6. Exploratory Objective of Study J2X-MC-PYAH, Treatment Arms 7-8

The exploratory objective is	
Characterize emergence of viral resistance to	Comparison from baseline to the last evaluable
LY3819253 in combination with VIR-7831	time point up to Day 29

Table PYAH.4.7. Exploratory Objective of Study J2X-MC-PYAH, Treatment Arms 9-11

The exploratory objective is	
Characterize emergence of viral resistance to	Comparison from baseline to the last evaluable
LY3853113	time point up to Day 29

Table PYAH.4.8. Exploratory Objective of Study J2X-MC-PYAH, Treatment Arms 12-14

The exploratory objective is	
Characterize emergence of viral resistance to	Comparison from baseline to the last evaluable
LY3853113	time point up to Day 29

[figure not shown]
Exploratory objectives not previously defined in the protocol are described in Section 6.16.2.

5. Study Design

5.1. Summary of Study Design

This is a Phase 2, randomized, single-dose study in participants with mild to moderate COVID-19 illness. Treatment Arms 1-11 are double-blind and placebo controlled, and Treatment Arms 12 and 14 are open-label.

5.1.1. Design Outline

Abbreviations: PD = pharmacodynamic; PYAH = Study J2X-MC-PYAH; SARS-CoV-2 = severe acute respiratory syndrome coronavirus 2.

Figure PYAH.5.1. Overview of participant flow from time of SARS-CoV-2 symptoms to treatment administration.

5.1.2. Screening

Interested participants will sign the appropriate informed consent and child/adolescent assent document(s), as appropriate, prior to completion of any procedures. The participant may enter the study with a previous positive SARS-CoV-2 viral test result from an external testing facility. This test result must be the first time the participant has tested positive for SARS-CoV-2.

The investigator will review symptoms, risk factors and other non-invasive inclusion and exclusion criteria prior to any invasive procedures. If the participant is eligible after this review, then the site will perform the invasive procedures to confirm eligibility.

5.1.3. Double-Blind Treatment and Assessment Period

This is the general sequence of events during the treatment and assessment period:

- Complete baseline procedures and sample collection
- Participants are randomized to an intervention group
- Participants receive study intervention, and
- Complete all safety monitoring and post-infusion sample collection.

Table PYAH.5.1 describes the planned Treatment Arms.

Table PYAH.5.1. Treatment Arms of Study J2X-MC-PYAH

Treatment Arms	Dose	Intervention	Participant Population
1		Placebo	
2	175 mg + 350 mg	LY3819253 + LY3832479	
3	700 mg + 1400 mg	LY3819253 + LY3832479	
4	2800 mg + 2800 mg	LY3819253 + LY3832479	
5	700 mg	LY3819253	
6	350 mg + 700 mg	LY3819253 + LY3832479	
7	700 mg + 500 mg	LY3819253 + VIR-7831	
8		Placebo	
9	175 mg	LY3853113	Low risk
10	175 mg + 700 mg + 1400 mg	LY3853113 + LY3819253 + LY3832479	Low risk
11		Placebo	Low risk
12	175 mg	LY3853113	High riska
13	175 mg + 700 mg + 1400 mg	LY3853113 + LY3819253 + LY3832479	High riska
14	175 mg + 700 mg + 1400 mg	LY3853113 + LY3819253 + LY3832479	High risk ^b

a See Protocol Section 5.1, Inclusion Criteria 27 and 28, for the definition of high-risk participants applicable for Treatment Arms 12 and 13.

Treatment Arm 1 is the corresponding placebo control for Treatment Arms 2-6.

Treatment Arm 8 is the corresponding placebo control for Treatment Arm 7.

Treatment Arm 11 is the corresponding placebo control for Treatment Arms 9 and 10.

5.1.4. Posttreatment Follow-up

Posttreatment follow-up assessments will be conducted at Day 60 and Day 85 to assess clinical status and for adverse events. Strategies to manage infection risks and reduce the burden of return visits may be used by sites, such as home visits.

Sample size was determined based on a pairwise comparison of LY3819253 in combination with VIR-7831 compared to placebo. An assumed sample size of 100 participants in Treatment Arms 7 and 8 provides greater than 87% power to test the superiority at the two-sided 0.05 alpha level on the proportion of participants with SARS-CoV-2 viral load greater than 5.27 at Day 7 (+2 days). This assumes the true underlying proportion of participants meeting this endpoint is 5% in the LY3819253 700 mg + VIR-7831 500-mg treatment arm and 19% in the placebo arm.

The sample size calculations were performed using simulations from the software EAST[©] v6.5.

Periodic adjustments to the allocation ratio of participants, informed by planned interim. See Protocol Section 9.5 for details.

Treatment Arms 9-11

The planned sample size is approximately 122 participants per treatment arm.

Sample size was determined based on pairwise comparisons of each dose compared to placebo. An assumed sample size of 122 participants per treatment arm provides about 84% power to test the superiority of either LY3853113 alone or the combination with LY3819253 and LY3832479 versus placebo at the two-sided 0.05 alpha level on the proportion of participants with SARS-CoV-2 viral load greater than 5.27 at Day 7. This assumes the true underlying proportion of participants meeting this endpoint is 12% in both the LY3853113 alone treatment arm and the LY3853113 + LY3819253 + LY3832479 combination treatment arm, and 28% in the placebo arm.

Treatment Arms 12-14

Approximately 100 participants will be enrolled into Treatment Arm 12 and approximately 50 participants will be enrolled into Treatment Arm 13. Treatment Arm 12 includes a greater number of participants to assess the tolerability of undiluted LY3853113 administration.

Approximately 140 participants will be enrolled into Treatment Arm 14 once Treatment Arms 12 and 13 have completed enrollment.

5.3. Method of Assignment to Treatment

5.3.1. Randomization

All participants will be centrally randomized to study intervention using an interactive webresponse system (IWRS). Before the study is initiated, the log-in information and directions for the IWRS will be provided to each site.

For Treatment Arms 1-13, participants will be stratified by duration since symptom onset to randomization (≤8 days vs >8 days). For Treatment Arms 12-13, participants will also be stratified by whether a participant received a SARS-CoV-2 vaccine or not prior to screening.

All eligible participants will be randomized, initially following an equal allocation to Treatment Arms. Periodic adjustments to the allocation ratio, informed by planned interim analyses, may be made to in an effort to achieve an equal allocation across the Treatment Arms at the end of enrollment. Given the staggered start of Treatment Arms, additional participants may be enrolled in existing Treatment Arms and the allocation ratio may change accordingly. See Protocol Section 9.5 for details.

5.3.2. Blinding

Treatment Arms 1-11 are double-blinded. Neither participants, nor investigators, nor the sponsor study team will be aware of treatment assignments prior to the final data base lock at the conclusion of the study.

Table PYAH.5.2 describes general procedures for unblinding.

Table PYAH.5.2. Unblinding Procedures for Study J2X-MC-PYAH

Unblinding (IWRS)	 Emergency unblinding for adverse events may be performed through the
	IWRS. All actions resulting in an unblinding event are recorded and reported
	by the IWRS
	 In case of an emergency, the investigator has the sole responsibility for
	determining if unblinding of a participants' intervention assignment
	is warranted
	 Participant safety must always be the first consideration in making such a
	determination. However, the investigator should make all attempts to contact
	the Medical Monitor in advance of unblinding
	• If a participant's intervention assignment is unblinded, the sponsor must be
	notified immediately after breaking the blind even if consultation occurred in
	advance
	The date and reason that the blind was broken must be recorded in the source
	documentation and case report form
	documentation and case report form

Abbreviation: IWRS = interactive web-response system.

If an investigator, site personnel performing assessments, or participant is unblinded while the infusion is ongoing, the participant must be discontinued from the study intervention and the

infusion stopped. If any amount of study intervention was administered, follow procedures according to the Schedule of Activities (SoA).

6. A Priori Statistical Methods

6.1. General Considerations

Statistical analysis of this study will be the responsibility of the sponsor or its designee.

All tables, figures, and listings will be created using the clinical trial database (unless otherwise noted), including data during study participation. While not reflected in a table, figure, or listing, any data collected after study participation (e.g., in the Eli Lilly and Company [Lilly] Safety System or collected through queries to the investigator) may be discussed in a clinical study report (CSR) or integrated summary document when deemed relevant.

Unless otherwise noted, displays will include columns for each treatment group, and in case of multiple doses of investigational product (IP), another column for IP doses combined will be displayed.

Not all displays described in this statistical analysis plan (SAP) will necessarily be included in the CSR. Not all displays will necessarily be created as a "static" display. Some may be incorporated into interactive display tools instead of, or in addition to, a static display. Any display described in this SAP and not provided would be available upon request.

For a binary endpoint collected in a longitudinal fashion, a generalized linear mixed-effect model may be applied assuming missing at random (MAR) if deemed appropriate.

Analyses will be performed separately for Treatment Arms:

- 1-6
- 7 and 8,
- 9-11,
- 12 and 13, and
- 14.

For Treatment Arms 12-14, participants who have received a SARS-CoV-2 vaccine prior to screening may be summarized separately from those who have not received a SARS-CoV-2 vaccine prior to screening, for all efficacy and safety outcomes. Additionally, participants who are \geq 12 and \leq 18 years old may be summarized separately than those who are \geq 18 years old.

All statistical analyses will be performed using SAS software Version 9.4 (or a higher version), FACTS 6.0 (or a higher version), and/or R 3.6 (or a higher version).

6.1.1. Analysis Populations

Patient populations are defined in Table PYAH.6.1 along with the analysis to be used to conduct. The treatment groups and inferential comparisons described in Table PYAH.6.1 will be used unless otherwise specified. Also, unless otherwise specified, for all populations/analysis, participants will be analyzed according to the treatment to which they were assigned.

Table PYAH.6.1. Analysis Populations

Population	Description
Entered	Definition: All participants who signed informed consent.
	Purpose: Used for disposition analysis.
	Treatment Groups: None
	Inferential Comparisons: None
Efficacy	Definition: All randomized participants who received study intervention and
	provided at least 1 postbaseline measure viral load measurement. Participants
	will be analyzed according to the intervention to which they were randomized
	(Intention to treat).
	Purpose: Used for efficacy and pharmacodynamic variables analyses.
	Treatment Groups (Short Label):
	Treatment Arms 1-6:
	175 mg LY3819253 and 350 mg LY3832479 (175/350 LY/LY2), 350
	mg LY3819253 and 700 mg LY3832479 (350/700 LY1/LY2), 700 mg
	LY3819253 and 1400 mg LY3832479 (700/1400 LY/LY2), 2800 mg
	LY3819253 and 2800 mg LY3832479 (2800/2800 LY/LY2), 700 mg
	LY3819253 (700 LY), and placebo (Pbo).
	Treatment Arms 7-8:
	700 mg LY3819253 and 500 mg VIR-7831 (700/500 LY/VIR), and
	placebo (Pbo).
	Treatment Arms 9-11:
	175 mg LY3853113 (175 LY3), 175 mg LY3853113 + 700 mg
	LY3819253 + 1400 mg LY3832479 (LY3/LY/LY2), placebo (Pbo)
	Treatment Arms 12-13:
	175 mg LY3853113 (175 LY3) and 175 mg LY3853113 + 700 mg
	LY3819253 + 1400 mg LY3832479 (LY3/LY/LY2)
	Treatment Arm 14:
	175 mg LY3853113 + 700 mg LY3819253 + 1400 mg LY3832479
	(LY3/LY/LY2)
	Additional optional combination arm may be added if decided.
	Inferential Comparisons:
	Treatment Arms 1-6:
	Each LY dose versus placebo
	Treatment Arms 7-8:
	700/500 LY/VIR dose versus placebo
	Treatment Arms 9-11:
	Each LY dose versus placebo
	Treatment Arms 12-14:
	None
Safety	Definition: All participants randomly assigned and who received any amount of
	study intervention. Participants will be analyzed according to the intervention
	they actually received.
	Purpose: Used for safety analyses, analyses of COVID-19-related
	hospitalization or death from any cause.
	Treatment Groups (Short Label):
	Treatment Arms 1-6:
	175 mg LY3819253 and 350 mg LY3832479 (175/350 LY/LY2), 350
	mg LY3819253 and 700 mg LY3832479 (350/700 LY1/LY2), 700 mg

	LY3819253 and 1400 mg LY3832479 (700/1400 LY/LY2), 2800 mg
	LY3819253 and 2800 mg LY3832479 (2800/2800 LY/LY2), 700 mg
	LY3819253 (700 LY), LY2 total, LY1/LY2 total, and placebo (Pbo).
	Treatment Arms 7-8:
	700 mg LY3819253 and 500 mg VIR-7831 (700/500 LY/VIR), and
	placebo (Pbo).
	Treatment Arms 9-11:
	175 mg LY3853113 (175 LY3), 175 mg LY3853113 + 700 mg
	LY3819253 + 1400 mg LY3832479 (LY3/LY/LY2), placebo (Pbo)
	Treatment Arms 12-13:
	175 mg LY3853113 (175 LY3) and 175 mg LY3853113 + 700 mg
	LY3819253 + 1400 mg LY3832479 (LY3/LY/LY2)
	Treatment Arms 14:
	175 mg LY3853113 + 700 mg LY3819253 + 1400 mg LY3832479 (LY3/LY/LY2)
	Additional optional combination arm may be added if decided.
	Inferential Comparisons:
	Treatment Arms 1-6:
	LY2 total versus placebo and 700 mg versus placebo
	Treatment Arms 7-8:
	700/500 LY/VIR dose versus placebo
	Treatment Arms 9-11:
	Each LY dose versus placebo
	Treatment Arms 12-14:
	None
Integrated Safety (Arms 9, 10,	Definition: All participants randomly assigned and who received any amount of
12-14)	study intervention in Arms 9, 10, or 12-14. Participants will be analyzed
	according to the intervention they actually received.
	Purpose: Used for safety analyses.
	Purpose: Used for safety analyses. Treatment Groups (Short Label):
	Purpose: Used for safety analyses. Treatment Groups (Short Label): Treatment Arms 9 and 12:
	Purpose: Used for safety analyses. Treatment Groups (Short Label): Treatment Arms 9 and 12: 175 mg LY3853113 (175 LY3)
	Purpose: Used for safety analyses. Treatment Groups (Short Label): Treatment Arms 9 and 12: 175 mg LY3853113 (175 LY3) Treatment Arms 10 and 13-14:
	Purpose: Used for safety analyses. Treatment Groups (Short Label): Treatment Arms 9 and 12: 175 mg LY3853113 (175 LY3) Treatment Arms 10 and 13-14: 175 mg LY3853113 + 700 mg LY3819253 + 1400 mg LY3832479
	Purpose: Used for safety analyses. Treatment Groups (Short Label): Treatment Arms 9 and 12: 175 mg LY3853113 (175 LY3) Treatment Arms 10 and 13-14: 175 mg LY3853113 + 700 mg LY3819253 + 1400 mg LY3832479 (LY3/LY/LY2)
	Purpose: Used for safety analyses. Treatment Groups (Short Label): Treatment Arms 9 and 12: 175 mg LY3853113 (175 LY3) Treatment Arms 10 and 13-14: 175 mg LY3853113 + 700 mg LY3819253 + 1400 mg LY3832479 (LY3/LY/LY2) Inferential Comparisons:
Pharmacokinetic and PK/PD	Purpose: Used for safety analyses. Treatment Groups (Short Label): Treatment Arms 9 and 12: 175 mg LY3853113 (175 LY3) Treatment Arms 10 and 13-14: 175 mg LY3853113 + 700 mg LY3819253 + 1400 mg LY3832479 (LY3/LY/LY2) Inferential Comparisons: None
Pharmacokinetic and PK/PD	Purpose: Used for safety analyses. Treatment Groups (Short Label): Treatment Arms 9 and 12: 175 mg LY3853113 (175 LY3) Treatment Arms 10 and 13-14: 175 mg LY3853113 + 700 mg LY3819253 + 1400 mg LY3832479 (LY3/LY/LY2) Inferential Comparisons: None Definition: All randomized participants who received study intervention and
(exposure-response	Purpose: Used for safety analyses. Treatment Groups (Short Label): Treatment Arms 9 and 12: 175 mg LY3853113 (175 LY3) Treatment Arms 10 and 13-14: 175 mg LY3853113 + 700 mg LY3819253 + 1400 mg LY3832479 (LY3/LY/LY2) Inferential Comparisons: None Definition: All randomized participants who received study intervention and have at least 1 postdose PK sample. Participants will be analyzed according to
	Purpose: Used for safety analyses. Treatment Groups (Short Label): Treatment Arms 9 and 12: 175 mg LY3853113 (175 LY3) Treatment Arms 10 and 13-14: 175 mg LY3853113 + 700 mg LY3819253 + 1400 mg LY3832479 (LY3/LY/LY2) Inferential Comparisons: None Definition: All randomized participants who received study intervention and have at least 1 postdose PK sample. Participants will be analyzed according to the intervention they received.
(exposure-response	Purpose: Used for safety analyses. Treatment Groups (Short Label): Treatment Arms 9 and 12: 175 mg LY3853113 (175 LY3) Treatment Arms 10 and 13-14: 175 mg LY3853113 + 700 mg LY3819253 + 1400 mg LY3832479 (LY3/LY/LY2) Inferential Comparisons: None Definition: All randomized participants who received study intervention and have at least 1 postdose PK sample. Participants will be analyzed according to the intervention they received. Purpose: Used for PK analyses.
(exposure-response	Purpose: Used for safety analyses. Treatment Groups (Short Label): Treatment Arms 9 and 12: 175 mg LY3853113 (175 LY3) Treatment Arms 10 and 13-14: 175 mg LY3853113 + 700 mg LY3819253 + 1400 mg LY3832479 (LY3/LY/LY2) Inferential Comparisons: None Definition: All randomized participants who received study intervention and have at least 1 postdose PK sample. Participants will be analyzed according to the intervention they received.
(exposure-response	Purpose: Used for safety analyses. Treatment Groups (Short Label): Treatment Arms 9 and 12: 175 mg LY3853113 (175 LY3) Treatment Arms 10 and 13-14: 175 mg LY3853113 + 700 mg LY3819253 + 1400 mg LY3832479 (LY3/LY/LY2) Inferential Comparisons: None Definition: All randomized participants who received study intervention and have at least 1 postdose PK sample. Participants will be analyzed according to the intervention they received. Purpose: Used for PK analyses. Treatment Groups (Short Label):
(exposure-response	Purpose: Used for safety analyses. Treatment Groups (Short Label): Treatment Arms 9 and 12: 175 mg LY3853113 (175 LY3) Treatment Arms 10 and 13-14: 175 mg LY3853113 + 700 mg LY3819253 + 1400 mg LY3832479 (LY3/LY/LY2) Inferential Comparisons: None Definition: All randomized participants who received study intervention and have at least 1 postdose PK sample. Participants will be analyzed according to the intervention they received. Purpose: Used for PK analyses. Treatment Groups (Short Label): Treatment Arms 1-6:
(exposure-response	Purpose: Used for safety analyses. Treatment Groups (Short Label): Treatment Arms 9 and 12: 175 mg LY3853113 (175 LY3) Treatment Arms 10 and 13-14: 175 mg LY3853113 + 700 mg LY3819253 + 1400 mg LY3832479 (LY3/LY/LY2) Inferential Comparisons: None Definition: All randomized participants who received study intervention and have at least 1 postdose PK sample. Participants will be analyzed according to the intervention they received. Purpose: Used for PK analyses. Treatment Groups (Short Label): Treatment Arms 1-6: 175 mg LY3819253 and 350 mg LY3832479 (175/350 LY/LY2), 350
(exposure-response	Purpose: Used for safety analyses. Treatment Groups (Short Label): Treatment Arms 9 and 12: 175 mg LY3853113 (175 LY3) Treatment Arms 10 and 13-14: 175 mg LY3853113 + 700 mg LY3819253 + 1400 mg LY3832479 (LY3/LY/LY2) Inferential Comparisons: None Definition: All randomized participants who received study intervention and have at least 1 postdose PK sample. Participants will be analyzed according to the intervention they received. Purpose: Used for PK analyses. Treatment Groups (Short Label): Treatment Arms 1-6: 175 mg LY3819253 and 350 mg LY3832479 (175/350 LY/LY2), 350 mg LY3819253 and 700 mg LY3832479 (350/700 LY1/LY2), 700 mg LY3819253 and 1400 mg LY3832479 (700/1400 LY/LY2), 2800 mg LY3819253 and 2800 mg LY3832479 (2800/2800 LY/LY2), 700 mg
(exposure-response	Purpose: Used for safety analyses. Treatment Groups (Short Label): Treatment Arms 9 and 12: 175 mg LY3853113 (175 LY3) Treatment Arms 10 and 13-14: 175 mg LY3853113 + 700 mg LY3819253 + 1400 mg LY3832479 (LY3/LY/LY2) Inferential Comparisons: None Definition: All randomized participants who received study intervention and have at least 1 postdose PK sample. Participants will be analyzed according to the intervention they received. Purpose: Used for PK analyses. Treatment Groups (Short Label): Treatment Arms 1-6: 175 mg LY3819253 and 350 mg LY3832479 (175/350 LY/LY2), 350 mg LY3819253 and 700 mg LY3832479 (350/700 LY1/LY2), 700 mg LY3819253 and 1400 mg LY3832479 (700/1400 LY/LY2), 2800 mg

700 mg LY3819253 and 500 mg VIR-7831 (700/500 LY/VIR), and placebo (Pbo).

Treatment Arms 9-11:

175 mg LY3853113 (175 LY3), 175 mg LY3853113 + 700 mg LY3819253 + 1400 mg LY3832479 (LY3/LY/LY2), placebo (Pbo)

Treatment Arms 12-13:

175 mg LY3853113 (175 LY3) and 175 mg LY3853113 + 700 mg LY3819253 + 1400 mg LY3832479 (LY3/LY/LY2)

Treatment Arm 14:

175 mg LY3853113 + 700 mg LY3819253 + 1400 mg LY3832479 (LY3/LY/LY2)

Additional optional combination arm may be added if decided.

Inferential Comparisons:

Treatment Arms 1-6:

Each LY dose versus placebo

Treatment Arms 7-8:

700/500 LY/VIR dose versus placebo

Treatment Arms 9-11:

Each LY dose versus placebo

Treatment Arms 12-14:

None

Per-Protocol

Definition: All participants in the efficacy population who do not meet any of the following criteria:

- received medication other than the medication the participant was randomized to:
- did not meet an inclusion criterion; or
- meet an exclusion criterion.

Purpose: Used for sensitivity analyses for the primary endpoint and the following secondary endpoints:

- change from baseline in viral load to Day 7,
- if there are a sufficient number of events, COVID-19 related hospitalization or death from any cause,
- if there are a sufficient number of events, COVID-19 related hospitalization, COVID-19 related emergency room visit, or death from any cause,
- · time to symptom resolution

Treatment Groups (Short Label):

Treatment Arms 1-6:

175 mg LY3819253 and 350 mg LY3832479 (175/350 LY/LY2), 350 mg LY3819253 and 700 mg LY3832479 (350/700 LY1/LY2), 700 mg LY3819253 and 1400 mg LY3832479 (700/1400 LY/LY2), 2800 mg LY3819253 and 2800 mg LY3832479 (2800/2800 LY/LY2), 700 mg LY3819253 (700 LY), and placebo (Pbo).

Treatment Arms 7-8:

700 mg LY3819253 and 500 mg VIR-7831 (700/500 LY/VIR), and placebo (Pbo).

Treatment Arms 9-11:

175 mg LY3853113 (175 LY3), 175 mg LY3853113 + 700 mg LY3819253 + 1400 mg LY3832479 (LY3/LY/LY2), placebo (Pbo)

Treatment Arms 12-13:

175 mg LY3853113 (175 LY3) and 175 mg LY3853113 + 700 mg
 LY3819253 + 1400 mg LY3832479 (LY3/LY/LY2)

Treatment Arm 14:

175 mg LY3853113 + 700 mg LY3819253 + 1400 mg LY3832479
 (LY3/LY/LY2)

Additional optional combination arm may be added if decided.

Inferential Comparisons:

Treatment Arms 1-6:
 Each LY dose versus placebo

Treatment Arms 7-8:
 700/500 LY/VIR dose versus placebo

Treatment Arms 9-11:
 Each LY dose versus placebo

Treatment Arms 12-14:
 None

Abbreviations: LY = study drug; PD = pharmacodynamic; PK = pharmacokinetic.

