6.10.3. Secondary Efficacy Analyses

6.10.3.1. SARS-CoV-2 Viral Load

6.10.3.1.1. Change from Baseline in SARS-CoV-2 Viral Load

Changes from baseline to Day 3, Day 5, Day 7, and Day 11 in SARS-CoV-2 viral load data in the log base 10 scale will be statistically analyzed using a linear mixed-effect model. The model will contain log base 10 transformed baseline as a covariate, treatment, day, treatment-by-day interaction) as fixed effects. The LS means and treatment differences (active treatment minus placebo) will be calculated and presented with their corresponding 95% CIs. In addition, the geometric mean ratio to baseline and corresponding standard error for each treatment, the ratio of geometric mean ratio to baseline vs placebo, and corresponding 95% CIs will be presented. All available data will be used in the analysis.

SARS-CoV-2 viral load, including changes from baseline, will be summarized and plotted by treatment and listed. Baseline is defined as the Day 1 predose assessment.

No imputations of missing data will be conducted.

6.10.3.1.2. SARS-CoV-2 Viral Load Among Participants Enrolled with ≤8 Days of Symptoms Prior to Randomization

Similar methodology, as described in Section 6.10.1, will be utilized on the subset of participants enrolled with ≤ 8 days of symptoms prior to randomization.

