6.10.3.3. Participant Clinical Status

6.10.3.3.1. COVID-19-Related Hospitalization or Death from Any Cause

Proportion (percentage) of participants who experience any of the following by Day 29 will be analyzed:

- COVID-19-related hospitalization (defined as ≥24 hours of acute care), or
- Death from any cause

The proportion of participants that experience hospitalization or death from any cause by Day 29 will be summarized by treatment in frequency tables and listed.

In addition, the number of participants that experience COVID-19 hospitalization or death from any cause by Day 29 will be analyzed using logistic regression to compare active treatment versus placebo at each dose level. If the number of observed events is less than 5 in any treatment arm an exact test (i.e. Fisher's exact) will be conducted instead of using a logistic regression. Data will not be imputed due to dropouts or missing data.

Proportion (percentage) of participants who experience COVID-19 related hospitalization or death from any cause by Days 22, 60, and 85 will also be analyzed.

The safety population will be utilized to analyze COVID-19-related hospitalization or death from any cause.

Based on the 'Hospitalization Events' eCRF page, a COVID-19-related hospitalization event is defined as an event with:

'Reason for Health Care Visit' of 'Primary Study Condition'

AND

- a 'Health Care Service Type' of:
 - o 'General Ward' or 'ICU'

OR

o 'Emergency Room' with a duration of \ge 24 hours.

6.10.3.3.1.1. Bayesian Modeling for COVID-19-Related Hospitalization or Death From Any Cause

Additionally, a Bayesian sensitivity analysis will be performed. A Bayesian logistic regression model will be fitted to evaluate the success criteria by the Lilly statistics group with the model listed below:

$$r_{ij} \sim Binomial(p_{ij}, 1)$$

$$\log\left(\frac{p_{ij}}{1 - p_{ij}}\right) = \alpha_i$$

Where,

 r_{ij} : is 1 if patient j on treatment i was hospitalized and 0 otherwise α_i : a parameter corresponding to treatment i (with i=1 being the placebo group). and priors:

$$\alpha_1 \sim \pi(\alpha_1)$$

At least 2 priors $(\pi(\alpha_1))$ will be considered for α_1 , a diffuse $N(0,100^2)$ and an informative prior based on available information at the time of analysis.

The safety population will be utilized to analyze COVID-19-related deterioration.

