6.10.3.3.2. COVID-19-Related Hospitalization, Emergency Room Visit, or Death From Any Cause

Proportion (percentage) of participants who experience any of the following by Day 29 will be analyzed:

- COVID-19-related hospitalization (defined as ≥24 hours of acute care),
- COVID-19 related emergency room visit, or
- death from any cause

The proportion of participants that experience COVID-19 related hospitalization, emergency room visit, or death from any cause by Day 29 will be summarized by treatment in frequency tables and listed.

In addition, the number of participants that experience COVID-19 related hospitalization, emergency room visit, or death from any cause by Day 29 will be analyzed using logistic regression to compare active treatment versus placebo at each dose level. If the number of observed events is less than 5 in any treatment arm an exact test (i.e. Fisher's exact) will be conducted instead of using a logistic regression. Data will not be imputed due to dropouts or missing data.

Proportion (percentage) of participants who experience COVID-19 related hospitalization, emergency room visit, or death from any cause by Days 22, 60, and 85 will also be analyzed.

The safety population will be utilized to analyze COVID-19 related hospitalization, emergency room visit, or death from any cause.

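### The Per-Protocol sensitivity analyses of the two clinical-status endpoints require a post-baseline viral load that their main analyses do not, so they differ by swab availability as well as by deviations

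*SAP*

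**What the plan says.** Four parts of the SAP bear on this.

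- **Per-Protocol set (Section 6.1.1, Table PYAH.6.1).** It consists of "All participants in the efficacy population who do not meet any of" three criteria. One is that the participant "received medication other than the medication the participant was randomized to"; the others are failing an inclusion criterion and meeting an exclusion criterion. None concerns swabs.
- **Efficacy population (same table).** Participants must be randomised, have received study intervention, and have "provided at least 1 postbaseline measure viral load measurement".
- **Use of the Per-Protocol set (same table).** The listed sensitivity analyses include "if there are a sufficient number of events, COVID-19 related hospitalization or death from any cause". The composite that adds emergency room visits is listed on the same condition.
- **Main analyses.** Section 6.10.3.3.1 states: "The safety population will be utilized to analyze COVID-19-related hospitalization or death from any cause". Section 6.10.3.3.2 states: "The safety population will be utilized to analyze COVID-19 related hospitalization, emergency room visit, or death from any cause". The Safety population is "All participants randomly assigned and who received any amount of" study intervention, with no swab requirement.

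No other text gives the clinical-status sensitivity analyses a different parent set.

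**The concern.** A per-protocol sensitivity analysis is read as answering one question: does the result hold once ineligible and wrongly treated participants are set aside? Here a second filter is applied as well, namely having a post-baseline viral load. That filter is not a deviation, and it can depend on the outcome, because a participant who dies before the first post-treatment swab cannot provide one.

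If the sensitivity result differs from the main result, the difference cannot be put down to deviations alone. If the two agree, the reassurance is weaker than it looks unless the number lost through missing swabs is known. The plan itself expects few events: it makes these analyses conditional on event numbers and moves to Fisher's exact test when any arm has fewer than 5. With counts that small, one or two lost events can shift the estimate visibly.

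**Working it through.** **Step 1: trace the sets.** The SAP states no event rate, event timing or count of unswabbed participants for these endpoints, so there is no planned figure to reproduce. The check is of the definitions.

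| Condition | Safety (main analysis) | Per-Protocol (sensitivity) |
|---|---|---|
| Randomised | required | required |
| Received study intervention | any amount | required |
| At least one post-baseline viral load | not required | required, through the Efficacy population |
| None of the three listed criteria | not required | required |

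Only the last row expresses eligibility or treatment deviation. The third row is inherited.

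**Step 2: who falls in the gap.** Section 6.10.3.1.1 analyses "Changes from baseline to Day 3, Day 5, Day 7, and Day 11 in SARS-CoV-2 viral load data", so the first analysed post-baseline viral load is Day 3. A dosed, eligible, correctly treated participant who has an event before any post-baseline swab and never has one later is an event under Safety and is absent under Per-Protocol. For a death before the first swab, the exclusion is certain. For an early admission, it happens only if no later swab is obtained.

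**Step 3: what a loss would do.** All event counts here are assumed. The arm sizes are the planned 150 for placebo and 100 for a single dose (Section 5.2, Arms 1-6). The comparison is each dose against placebo, which is what the Per-Protocol row lists. If k placebo participants with events lack every swab, the placebo rate becomes (9 - k)/(150 - k). The difference is that rate minus 1/100, and p is from the two-sided Fisher's exact test.

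| Placebo events lost (k) | Placebo | Active | Difference (points) | p |
|---|---|---|---|---|
| 0 | 9/150 = 6.0% | 1/100 = 1.0% | 5.0 | 0.054 |
| 1 | 8/149 = 5.4% | 1.0% | 4.4 | 0.089 |
| 2 | 7/148 = 4.7% | 1.0% | 3.7 | 0.148 |
| 3 | 6/147 = 4.1% | 1.0% | 3.1 | 0.25 |
| 4 | 5/146 = 3.4% | 1.0% | 2.4 | 0.41 |

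The shift can go the other way. If only the single active event is lost, the data are 9/150 v 0/99, a difference of 6.0 - 0 = 6.0 points (Fisher p=0.013).

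A second assumed table uses the planned 122 per arm of Arms 9-11. Starting from 6/122 v 1/122 (4.1 points, p=0.12), losing one placebo event gives 3.3 points with p still 0.12, and losing three gives 1.7 points with p=0.37.

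No participant in any of these rows has a listed deviation.

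**The case against.** The strongest case against the point is that few participants may be affected, and that the consequence is limited.

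- **Only complete absence of a swab excludes.** Viral load or clearance is assessed on Days 3, 5, 7, 11 and 29, and Section 6.3 keeps out-of-window assessments in the analysis. One later result retains an early event. This stands. A reader might infer that the earliest and sickest events are removed as a class, but the definition does not do that.
- **Admission is not shown to stop swabbing.** Appendix 1 limits the symptom questionnaire to outpatients, but the SAP sets no such limit on swabs, and Appendix 4 expects some assessments on inpatients. This also stands. Loss of early deaths follows from the definitions; loss of early hospitalisations is possible but not established.
- **The reach is small.** These are conditional sensitivity analyses of secondary endpoints in a study that Section 6.5 calls nonconfirmatory. For hospitalisation or death, Section 6.10.3.3.1.1 adds a Bayesian sensitivity analysis on the Safety population. Arms 12-14 have no inferential comparison. All of this limits the weight of the point.
- **Agreement between the two analyses can still be informative.** If almost nobody lacks every swab, the parent sets nearly coincide. A reader might conclude that agreement never reassures; that goes too far.

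It is also tempting to illustrate the effect by pooling the combination arms against placebo. The Per-Protocol row for Arms 1-6 lists only each dose against placebo, so a pooled table would not represent this analysis.

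None of these arguments removes the mismatch in parent sets.

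**Conclusion.** The point holds as a mismatch of populations. Followed exactly, the plan compares a main analysis that needs no swab with a sensitivity analysis that does, and the added condition can depend on the outcome. The main analyses of both endpoints are unaffected.

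The size is unknown. In the Arms 1-6 illustration, losing one to four placebo events moves the difference by 0.6 to 2.6 points (from 5.0 to 4.4, and to 2.4), and losing the one active event moves it by 1.0 point the other way. With no such losses, nothing changes. These figures rest on assumed counts and show sensitivity to small losses; they do not predict the trial's data. A reader might infer a bias in a known direction, for instance against the active arms, but the SAP gives no basis for saying which arm would lose more events. This is a change worth making, not one on which the trial's conclusions depend.

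**What to change.** In Table PYAH.6.1, state that for hospitalisation or death, and for hospitalisation, emergency room visit or death, the Per-Protocol set is the Safety population minus participants meeting any of the three listed criteria. Keep the post-baseline viral load requirement for the viral-load endpoints only. Time to symptom resolution is not a clinical-status endpoint and its main analysis falls under the Efficacy population, so it does not have this mismatch; the row can simply name its parent set.

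The SAP already has a model for this. The addendum Efficacy population in Section 6.19.1 ties its post-baseline requirement to the endpoint being analysed. Because wrong-medication participants are excluded, analysis as randomised and analysis as treated coincide in the revised set.

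The cost is one sentence and one additional population flag, with no new data. It would also help to report, by arm, how many Safety participants have no post-baseline viral load and how many of them had an event, so that the effect of the requirement can be seen directly.
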